3.4. Enrollment Strategy

Study subjects will be recruited from the Institution/clinical site's subject database and utilizing Institutional Review Board (IRB) approved materials.

4. STUDY DESIGN AND RATIONALE

4.1. Description of Study Design

This study is a randomized, 2-visit, partially subject-masked, 2-arm parallel, dispensing trial. Approximately 236 subjects (118 subjects /arm) will be screened and enrolled to ensure that at least 224 subjects (112 subjects/arm) to complete.

The study begins with an initial visit (Visit 1). If a subject is found to meet all eligibility criteria, they will be randomized to one of two study lenses (Test or Control) in a bilateral fashion.

If the subject is dispensed study lenses at the initial visit, one follow-up visit will be conducted. The follow-up visit will occur approximately two weeks after the initial visit. Unscheduled followup visits may occur during the study. Subjects will be advised to wear the study lenses at least five (5) days per week for at least six (6) hours per day for a period of two weeks. There is no planned lens replacement scheduled for during this study.

4.2. Study Design Rationale

The purpose of this study is to provide evidence that the investigational contact lens, senofilcon A with new-UV blocker meets all criteria specified by the Customer Requirements Document (CRD). Since this contact lens was approved for daily wear at a replacement rate of 2-weeks, a parallel study design with a 2-week follow-up evaluation was chosen as the most optimal design to evaluate the criteria specified in the CRD.

4.3. Enrollment Target and Study Duration

- Approximately 112 subjects are targeted to complete the Test arm of the study, and an additional 112 subjects are targeted to complete the Control arm of the study.
- 10 clinical sites will be recruited to participate, and each site will enroll approximately 20-24 subjects.
- Enrollment is defined at the point when the Informed Consent is signed. Termination is defined at the completion of the Final Evaluation.
- Each site will have approximately 2 weeks to enroll all their subjects unless otherwise approved by the Sponsor. Each subject will be in the study approximately 2 weeks, making the entire study approximately 4 weeks in duration.

	Test	Control	Total
Randomization	116	116	232
Completion	112	112	224
Number of sites	10	10	10
Subjects/site (Min-Max)	10-12	10-12	20-24

Table 2: Target number of subjects by arm and site

5. TEST ARTICLE ALLOCATION AND MASKING

5.1. Test Article Allocation

A computer-generated randomization scheme will be used to randomly assign subjects, in blocks of 4, to one of the two possible study lenses (TEST or CONTROL). The random scheme will be generated using the PROC PLAN procedure from Statistical Analysis System (SAS) Software Version 9.4 or higher (SAS Institute, Cary, NC).

The study site must follow the randomization scheme provided and complete enrollment according to the randomization list and not pre-select or assign subjects. The randomized assignment of subjects will be performed at the first visit prior to the first fitting. The following must have occurred prior to randomization:

- Informed consent has been obtained
- Subject meets all the inclusion / not meets exclusion criteria
- Subject history and baseline information has been collected.

5.2. Masking

The dynamic nature of the Test lens makes it impossible to completely mask the study lens assignment. The subjects will be aware if they are wearing a photochromic lens or non-photochromic lens due to the function nature of the photochromic dye. Additionally, there is a slight difference in physical appearance between the Test and Control lenses when the Test lens is activated by outdoor light that makes it difficult to mask investigative personnel. However, the Control lens will be masked in the event that OASYS is the subject's habitual lens by chance, making this a partial-subject masked study.

Every attempt will be made to keep the other clinical trial personnel involved in the study (e.g. Data management, Biostatistician and Clinical Operations) unaware of the lens assignment. The identity of the study lenses will be masked by over labeling the blister packs with a label containing the study number, lot number, sphere power, expiration date and the randomization codes. Only the personnel involved in the over labeling and the Statistician generating the randomization scheme will have access to the decode information translating the randomization codes into Test and Control arms. The medical monitor will also have access to the decode information in case breaking the mask is necessary for the urgent medical treatment of a subject.

5.3. Procedures for Maintaining and Breaking the Masking

The test articles mask shall not be broken unless information concerning the lens type is necessary for the urgent medical treatment of a subject. The Sponsor must be notified before the mask is broken.

When dispensing test articles, the following steps should be followed to maintain randomization codes:

- 1. Investigator or designee (documented on the Delegation Log) will consult the lens fitting schedule/randomization scheme to obtain the test article assignment for that subject prior to dispensing
- 2. Investigator or designee will record the subject's number on the appropriate line of the randomization scheme
- 3. Investigator or designee will pull the appropriate test articles from the study supply. All test articles that are opened, whether dispensed (placed/fit on eye or dispensed outside the clinical site) or not, must be recorded on the Test Article Accountability Log in the "Dispensed" section

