6.4. Packaging and Labeling

The Control articles will be packaged in their commercial blister packs with investigational overlabel to mask their identity. The Test articles will be packaged in blisters as the primary packaging and labeled with investigational foil. The test articles will be in plastic bags as the secondary packaging form. The sample study label is shown below:

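### Sites work from a coded randomisation list with no described means of hiding its later lines, so coming assignments may be knowable before eligibility is decided

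*Protocol*

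**What the plan says.** Protocol 5.1 supplies the scheme to the site: "The study site must follow the randomization scheme provided and complete enrollment according to the randomization list and not pre-select or assign subjects". It also sets an order. Under "The following must have occurred prior to randomization" it lists consent, eligibility, and collection of history and baseline data. SAP 2.4 repeats both rules. The block size is 4 in Protocol 5.1 and 2 in SAP 2.4.

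Protocol 5.3 gives the working procedure. The investigator or designee "will consult the lens fitting schedule/randomization scheme to obtain the test article assignment for that subject prior to dispensing", must then "record the subject's number on the appropriate line of the randomization scheme", and finally pulls the lenses from the study supply.

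Protocol 5.2 covers masking: "The identity of the study lenses will be masked by over labeling the blister packs with a label containing the study number", together with lot number, sphere power, expiry date and randomisation code. The key from code to arm is limited to the over-labelling personnel, the statistician who generates the scheme, and the medical monitor. The same section accepts that subjects will know which type of lens they wear, and that site staff are hard to mask once the Test lens is activated outdoors.

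Protocol 6.4 describes the packs. For Control: "The Control articles will be packaged in their commercial blister packs with investigational overlabel to mask their identity". For Test: "The Test articles will be packaged in blisters as the primary packaging and labeled with investigational foil". Plastic bags are the secondary packaging. Table 3 lists a sterile blister pack for both lenses.

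**The concern.** Concealment is meant to ensure that whoever decides whether a subject enters the trial cannot know which arm comes next. Here the same site staff judge eligibility and handle the list.

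Several decisions before randomisation involve judgement. Exclusion 13 turns on the investigator's view of ocular abnormalities. Exclusion 14 turns on a Grade 2 slit lamp grading. Step 1.12 allows one further baseline attempt. The order in which subjects are seen is also left open. If the next lens is known, any of these can come to depend on it, and the arms may then differ before a lens is worn.

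All five primary hypotheses must be met, and four of them compare the arms. Protection from baseline adjustment is uneven:

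- **Comfort:** the model includes baseline CLUE comfort.
- **Acuity and bright-light satisfaction:** neither model has a baseline outcome term.
- **Slit lamp findings:** the SAP 10.1 text includes baseline findings, but the code in SAP 14.1 does not.

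**Working it through.** The plan states no figure on this point to reproduce. The check sets the provisions side by side and then sizes the risk.

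**1. Is there a list at the site?** Yes. Protocol 5.1 says the scheme is provided, and 5.3 has site staff consult it and write on the appropriate line. That describes a document with more than one line.

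**2. Is anything said to hide the later lines?** No. Protocol 5.1 and 5.3 and SAP 2.4 contain an instruction not to pre-select and a rule that eligibility comes first. These govern conduct and sequence; neither hides the next assignment. Interactive voice response appears only in the SAP abbreviation list. Protocol 15.1 describes the EDC system for data capture only.

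**3. Could staff infer the codes without the decode?** The documents leave four routes open.

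- The blisters are described differently: overlabelled commercial pack against investigational foil (6.4).
- Labels carry lot number and expiry date (5.2). Two different products would ordinarily have different lots, so packs might be grouped by arm. This is inference.
- Power is chosen at step 1.14 from 21 powers (6.1), so packs are unlikely to be pre-assigned to subjects and the code probably marks lens type. The number of codes per arm is not stated.
- One Test lens seen to darken would link its code to the arm, and so link every line bearing that code.

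**4. Does block size settle it?** Suppose first that staff know past assignments and the block length, but cannot read ahead.

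- *Block of 2:* the second position is always determined, so 1/2 of assignments are certain (116 of 232 randomised). Best-guess success is (0.5 + 1)/2 = 75.0%.
- *Block of 4:* there are six sequences and 24 positions. The last position is always determined (6), and the third is determined when the first two match (2). So 8/24 = 1/3 are certain (about 77 of 232). Best-guess success is (1/2 + 2/3 + 2/3 + 1)/4 = 70.8%.

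If later lines can be read and decoded, block size no longer matters. Reconciling 4 with 2 is needed anyway but would not close this gap.

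**5. Illustrative size for CLUE comfort.** Document inputs are the CLUE population SD of 20 (Protocol 2.2.1), 10 to 12 Test subjects per site (Protocol Table 2), and the margin of 5, SD of 21 and 112 per arm (Protocol 14.2). The assumption is that, at every site, one Test place goes to a subject who would score 20 points higher than the subject otherwise placed there.

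- Shift in Test mean = 20/n. For n = 12 this is 1.67 points; for n = 10 it is 2.0 points. That is 33% to 40% of the margin.
- Unadjusted SE of the difference = 21 × √(2/112) = 2.81.
- At a true difference of −5, the chance of falsely declaring non-inferiority is 1 − Φ(1.96 − shift/SE).
  - No shift: 2.5%.
  - 1.67 points: 1 − Φ(1.366) = 8.6%.
  - 2.0 points: 1 − Φ(1.247) = 10.6%.

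These are normal approximations without baseline adjustment. The planned comfort model would reduce the bias to the extent that selection acts through the baseline comfort score.

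**The case against.** The strongest reply is that the site's list shows codes, not arms, and that Protocol 5.2 deliberately withholds the key from sites. That is correct. A reader might infer from 5.3 that every future assignment is open to the site; the documents do not support this. Two links are unproven.

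- **Visibility of later lines.** Protocol 5.3 speaks of the appropriate line of a schedule whose format is not given. Open later lines are implied, not stated.
- **Distinguishable packs.** Protocol 6.4 says the Control overlabel is there to mask identity, 5.2 speaks of over-labelling the blister packs without limiting this to Control, and Table 3 puts both in the same category. The sample label to which 6.4 refers was not available in the text reviewed. The secondary plastic bags also appear to be common to both lenses.

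It is also fair to say that comfort, the endpoint used for the illustration, is the one explicitly adjusted for its own baseline score.

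What stands after all this is that the codes are the only thing described as keeping the next assignment from the site, and that the protocol's own account of the labels, packs and photochromic lens gives grounds to doubt that they suffice.

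**Conclusion.** The point holds as a gap in allocation concealment. The plan puts a coded, multi-line list in the hands of staff who decide eligibility, describes no mechanism that hides later lines, and relies on codes that may be inferable. Coming assignments may therefore be knowable before eligibility is settled, at either stated block size. The documents do not show that they are known, or that any site would act on such knowledge.

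The 1.7 to 2.0 point shift in mean comfort illustrates what a small amount of selection could do. It rests on an assumed 20-point advantage, one such placement at every site, selection always in favour of the Test lens, and no baseline adjustment. The planned comfort analysis would show less. For acuity and bright-light satisfaction there is no baseline outcome term to absorb a similar imbalance; its size there has not been estimated.

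This is a worthwhile, low-cost improvement rather than a flaw that by itself invalidates the trial.

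**What to change.** In Protocol 5.1 and 5.3, and correspondingly in SAP 2.4, replace consultation of a site-held list with release of one assignment at a time, after eligibility has been recorded at step 1.13. Sequentially numbered opaque sealed envelopes, opened at step 1.14 and marked with subject number, date and time, would do this. The EDC system is an alternative if it supports randomisation, which the protocol does not say.

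In Protocol 6.4, give both lenses' blisters the same outer label appearance, so that unopened stock does not suggest which code belongs to which lens.

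If later lines are already concealed in practice, 5.1 and 5.3 should say how.

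The cost is preparing the envelopes, adopting one label format and a short delay at step 1.14. No extra subjects are needed. The change protects the decision to enrol; it does not mask site staff after the lens is on the eye, which Protocol 5.2 already accepts is difficult.

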6. STUDY INTERVENTION

6.1. Identity of Test Articles

The following contact lenses will be used in this study:

Table 3: Test Articles

	Control	Test
Name	OASYS	ECL600
Manufacturer	JJVCI	JJVCI
Lens Material	senofilcon A	senofilcon A
Nominal Base Curve @ 22°C	8.4	8.4
Nominal Diameter @ 22°C	14.0	14.0
Nominal Distance Powers (D)	-1.00 to -6.00 in 0.25	-1.00 to -6.00 in 0.25
[1] D. E. L., C. Schulz, E. D. C., Sharin I. L. C. Ber, and the latter of the Physics of A 1984. ArXiv 10.	steps	steps
Water Content (%)	38	38
Center Thickness (-3.00 D)	0.070	0.085
Oxygen Permeability (Dk)	103	103
Modality in Current Study	Daily wear	Daily wear
Replacement Frequency	Single use	Single use
Packaging Form (vial, blister, etc.)	Sterile blister pack	Sterile blister pack

There are 21 powers (sku's) from -1.00 through -6.00 D. Approximately 90 lenses per sku will be made available based on the following factors: sample size, bilateral wear, biweekly replacement, safety margin of 2x, and US distribution model.

6.2. Ancillary Supplies/Products

The following solutions will be used in this study:

Table 4: Ancillary Supplies

	Solution 1	Solution 2
Solution Name / Description	Opti-Free [®] PureMoist [®]	Eye-Cept [®] Rewetting Drops
Lot Number or Other Identifier	Varies	Varies
Manufacturer	Alcon Laboratories, Fort Worth, TX	Optics Laboratories
Maximum Preservative	0.001% polyquaternium-1, 0.0006% myristamidopropyl dimethylamine	NA

[figure not shown]
6.3. Administration of Test Articles

Test articles will be dispensed to subject meeting all eligibility requirements, including any dispensing requirements set forth in this clinical protocol. Subjects will be dispensed an adequate supply of test articles to complete the study. Lost or damaged test articles may be replaced at the discretion of the Investigator and/or the Sponsor.

6.4. Packaging and Labeling

The Control articles will be packaged in their commercial blister packs with investigational overlabel to mask their identity. The Test articles will be packaged in blisters as the primary packaging and labeled with investigational foil. The test articles will be in plastic bags as the secondary packaging form. The sample study label is shown below:

6.5. Storage Conditions

Test articles will be maintained at ambient temperatures at the clinical site. Test articles must be kept under secure conditions and out of direct sunlight.

6.6. Collection and Storage of Samples

All worn study lenses will be collected from the subject, placed in labeled glass vials with Opti-Free[®] PureMoist[®], and stored refrigerated or frozen until they are shipped back to the Sponsor. The lenses will be shipped in special containers to keep the lenses refrigerated.

When possible, any lens or test article associated with an Adverse Events and/or a Product Quality Complaint must be retained and stored in a glass vial with moderate solution pending directions from the sponsor for potential return back to JJVCI.

6.7. Accountability of Test Articles

JJVCI will provide the Investigator with sufficient quantities of study articles and supplies to complete the investigation. The Investigator is asked to retain all lens shipment documentation for the test article accountability records.

Test article must be kept in a locked storage cabinet, accessible only to those assigned by the Investigator for dispensing. The Investigator may delegate this activity to authorized study site personnel listed on the Site Delegation Log. All test articles must be accounted. This includes:

- 1. What was dispensed for the subject for trial fitting, to wear out of the office, or issued for the subject to replace appropriately between visits
- 2. What was returned to the Investigator unused
- 3. The number and reason for unplanned replacements

Following final reconciliation of test articles by the monitor, the Investigator or monitor will return all unused test articles to JJVCI.

If there is a discrepancy between the shipment documents and the contents, contact the study monitor immediately.

7. STUDY EVALUATIONS

7.1. Time and Event Schedule

Table 5: Time and Events

Visit Information	Visit 1 Screening, Baseline, Treatment 1	Visit 2 Follow-up, Final Evaluation
Time Point	Day 1	Day 14 ± 1
Estimated Visit Duration	2.5 hours	1.5 hours
Statement of Informed Consent	X	1.0 10000
Demographics	X	
Medical History/Concomitant Medications	X	X
Habitual Contact Lens Information	Х	
Inclusion/Exclusion Criteria	X	
Baseline Questionnaires	X	
Entrance Visual Acuity	X	
Iris Color	Х	
Keratometry	Х	Х
Subjective Sphero-Cylindrical Refraction	X	Х
Slit Lamp Biomicroscopy	Х	X
Lens Selection	X	
Lens Insertion & Settling	Х	
Visual Acuity and Over Refraction	Х	
Lens Power Modification	Х	
Subject Reported Ocular Symptoms	X	Х
Visual acuity (distance Snellen)	Х	X
Lens Fit Assessment	Х	X
Lens Wettability	X	Х
Dispense Patient Instruction Guide	X	
Dispense Test Article	X	

Visit Information	Visit 1	Visit 2
	Screening, Baseline,	Follow-up,
	Treatment 1	Final Evaluation
Time Point	Day 1	Day 14 ± 1
Estimated Visit Duration	2.5 hours	1.5 hours
Lens wear Compliance		Х
Wearing Time and Compliance		X
Follow-up Questionnaire		Х
Distance ETDRS logMAR Visual Acuity		Х
Surface Deposits		Х
Study Completion		Х
Lens Removal and Storage		Х
Final Evaluation		Х

7.2. Detailed Study Procedures

VISIT 1

The subjects must present to Visit 1 wearing their habitual contact lenses.

	Visit 1: Screening			
Step	Procedure	Details		
1.1	Statement of Informed Consent	Each subject must read, understand, and sign the Statement of Informed Consent before being enrolled into the study. The Principal Investigator or his/her designee conducting the informed consent discussion must also sign the consent form.		
r.		Note : The subject must be provided a signed copy of this document.		
1.2	Demographics	Record the subject's date of birth, gender, race and ethnicity.		
1.3	Medical History and Concomitant Medications	Questions regarding the subjects' medical history and concomitant medications.		
1.4	Habitual Lenses	Questions regarding the subject's habitual lens type and parameters.		
1.5	Eligibility after Screening	All responses to Screening Inclusion Criteria questions must be answered "yes" and all responses to Exclusion Criteria must be answered "no" for the subject to be considered eligible.		

	Visit 1: Screening			
Step	Step Procedure Details			
		If the subject is deemed to be ineligible after screening, proceed to Final Evaluation and complete Subject Disposition. Refraction and Biomicroscopy forms are not required.		

	Visit 1: Baseline			
Step	Procedure	Details		
1.6	Baseline Questionnaire	The subject will respond to the CLUE Baseline Questionnaire.		
1.7	Entrance Visual Acuity	Record the distance Snellen visual acuity (OD, OS, and OU) to the nearest letter with their habitual contact lens correction in place. Subjects must read the smallest line until at least 50% of the letters are read incorrectly.		
1.8	Remove Habitual Lens	The subject's habitual lenses will be removed and stored in their own lens case. If they forgot to bring their lens case, one will be provided to them.		
1.9	Iris Color	The investigator will record the subject's iris color based on the scale provided.		
1.10	Keratometry	Record the keratometry readings OD and OS in diopters. This can come from any appropriate instrument so long as the same instrument is used at the Final Evaluation.		
1.11	Subjective Sphero- cylindrical Refraction	Complete subjective spherocylindrical refraction and record the resultant distance visual acuity (OD, OS, and OU) to the nearest letter. Best corrected distance visual acuity (BVA) must be 20/25+3 or better in each eye.		
1.12	Slit Lamp Biomicroscopy	FDA Slit Lamp Classification Scale will be used to grade the findings and determine eligibility. If any of these slit lamp findings are grade 2 or higher, the subject may not continue at this time, but may return up to one additional time to determine eligibility. If after a		
		total of 2 attempts the subject is deemed		

	Visit 1: Baseline			
Step	Procedure	Details		
0		ineligible, then complete the Final		
		Evaluation.		
		If the clearance of the fluorescein needs to be expedited, preservative-free rewetting drops or saline may be instilled.		
1.13	Eligibility after Baseline	All responses to Inclusion Criteria questions must be answered "yes" and all responses to Exclusion Criteria questions must be answered "no" for the subject to be considered eligible.		
		If subject is deemed to be ineligible after the first or second baseline, proceed to Final Evaluation and complete all forms.		

	Visit 1: Treatment 1 Lens Fitting			
Step	Procedure	Details		
1.14	Lens Selection	Assign the study lens based on the randomization scheme. Select the contact lens power based on subjective refraction. Record the test condition.		
1.15	Lens Insertion	The Investigator or the subject inserts the study lenses. Record the time of lens insertion. Check for lens damage under the slit lamp before proceeding with lens settling. Replace damaged lenses if applicable.		
1.16	Lens Settling	Allow the study lenses to settle for a minimum of 5 minutes.		
1.17	Subjective Best Sphere Over Refraction	Perform subjective best sphere refraction over the study lenses with a phoropter (adopt the maximum plus to maximum visual acuity (MPMVA) approach and use the duo-chrome, binocular blur, or other suitable test for binocular balancing) and record the best corrected distance Snellen visual acuity to the nearest letter (OD, OS, and OU).		

1	Visit 1: Treatment 1 Lens Fitting			
Step	Procedure	Details		
1.18	Lens Power Modification (if applicable)	Adjust the lens power if the subject's best sphere over-refraction is not plano. For each power modification, repeat steps (1.15-1.17). One power modification is allowed per eye.		
1.19	Time Interval	Please wait for at least 10 minutes from final lens insertion to continue.		
1.20	Subject Reported Ocular Symptoms	Subjects will respond to a verbal open-ended symptoms questionnaire.		
1.21	Visual Acuity	Record the distance Snellen visual acuity with the contact lenses (OD, OS, and OU) to the nearest letter. Smaller lines must be shown until the subject incorrectly identifies at least 50% of the letters.		
1.22	Subjective Lens Fit Assessment	 Evaluate overall lens fit acceptance (acceptable or unacceptable) based on centration, movement and other fitting characteristics. An unacceptable fit is deemed by one of the following criteria: limbal exposure at primary gaze or with extreme eye movement edge lift excessive movement in primary and up gaze insufficient movement in all three of the following conditions: primary gaze, up gaze, and Josephson push up Note: if lens fit is unacceptable subject will be discontinued from the study. 		
1.23	Lens Wettability	Perform the white light lens wettability procedure and record the results.		
1.24	Continuance	 For the subject to continue in the study, they must meet all three of the following criteria: Visual acuity is 20/30 or better OD and OS The lens fit is acceptable OD and OS Investigator approval. 		

Visit 1: Treatment 1 Lens Fitting			
Step	Procedure	Details	
		If the Investigator does not approve the dispensing of the first study lens based on subject feedback (e.g., unsatisfactory comfort), then the study is terminated for that subject.	
1.25	Dispense	 The lenses will be dispensed for 13-15 days 1. The subjects should wear their lenses similar to the inclusion criteria: ≥ 6 hours per day, ≥ 5 days per week. 2. The lenses will be worn as daily wear only. 3. All subjects will be provided Opti-Free PureMoist to be used in a rub regime. 4. Preservative-free rewetting drops are permitted if needed. 5. A patient instruction booklet will be provided. 6. The lenses must be stored in the supplied case out of direct sunlight. Note 1: In the event a lens is lost or damaged, the subject will return to the investigator site for replacement (extra lenses cannot be given at the dispensing visit). Note 2: The subject's habitual contact lenses cannot be worn at any time during the study. Note 3: Instruct subjects to bring their spectacles to the next visit. 	

VISIT 2

The follow-up will occur 13-15 days following Visit 1. The subjects must enter the visit wearing their study contact lenses.

	Visit 2: Treatment 1 Follow-Up 1			
Step	Procedure	Details		
2.1.	Adverse Events and Concomitant Medications Review	Review any changes to the subject's medical history or concomitant medications from the previous study visit. Record any changes, and any adverse events.		
2.2.	Wearing Time	Record the average wearing time and comfortable wearing time.		
2.3.	Compliance	Confirm compliance with the prescribed wear schedule.		
2.4.	Subject Reported Ocular Symptoms	Subjects will respond to a verbal open-ended symptoms questionnaire.		
2.5.	Follow-Up Questionnaires	The subject will respond to the Follow-Up Questionnaires.	1.5 2.5	
2.6.	Visual Acuity	Record the distance Snellen visual acuity with the contact lenses (OD, OS, and OU) to the nearest letter. Subjects must read the smallest line until at least 50% of the letters are read incorrectly.		
2.7.	Distance ETDRS LogMAR Visual Acuity	Perform 4 m distance ETDRS LogMAR visual acuity test OD and OS under the following conditions: Bright room illumination / high contrast charts a. Room illumination > 400 lux b. Chart luminance 120-200 cd/m ² c. One high contrast chart per eye. 1) OD: chart HC-1 2) OS: chart HC-2		
2.8.	Subjective Lens Fit Assessment	 Evaluate overall lens fit acceptance (acceptable or unacceptable) based on centration, movement and other fitting characteristics. An unacceptable fit is deemed by one of the following criteria: limbal exposure at primary gaze or with extreme eye movement edge lift 		

	Visit 2: Treatment 1 Follow-Up 1			
Step	Procedure	Details		
		 insufficient or excessive movement in all three of the following conditions: primary gaze, up gaze, and Josephson push up 		
2.9.	Lens Wettability	Perform the white light lens wettability procedure and record the results.		
2.10.	Surface Deposits	Record any front and back surface lens deposits.		
2.11.	Lens Removal & Storage	Both lenses will be removed and stored wet in a labeled container with Opti-Free PureMoist. The lenses can be stored refrigerated or frozen prior to shipment back to the Sponsor. Lenses will be stored at JJVCI for 45 days after LSLV for laboratory testing (Section 7.4).		
2.12.	Slit Lamp Biomicroscopy	 FDA Slit Lamp Classification Scale will be used to grade the findings. If the subject has a Grade 3 or higher slit lamp finding, it will be recorded as an Adverse Event and the subject will be followed to resolution. Adverse events must be reported to the JJVCI monitors immediately. If the clearance of the fluorescein needs to be expedited, preservative-free rewetting drops may be instilled. 		

FINAL EVALUATION

The final evaluation will ordinarily take place immediately following the last scheduled follow-up visit per the study protocol. It may also take place at any point the subject discontinues the study or is terminated from the study.

Final Evaluation			
Step	Procedure	Details	
F.1	Final Exam Form	Indicate if the subject completed the study successfully. If subject discontinued from the study, indicate the reason.	
F.2	Keratometry	Record the keratometry readings OD and OS in diopters. This can come from any appropriate instrument so long as the same instrument was used at the Baseline Evaluation.	

Final Evaluation			
Step	Procedure	Details	
F.3	Subjective spherocylindrical Refraction	Perform bare-eye subjective spherocylindrical refraction with a phoropter and record the best corrected distance visual acuity to the nearest letter (OD, OS, and OU).	

